## Scenario summary

research topic	Application of Single-Port Robot-Assisted Breast-Conserving Surgery via Axillary Approach for Breast Cancer.
Main purpose of the study	
1. To evaluate the efficacy of single-port robots in breast cancer breast conserving surgery. Including differences in operative time and intraoperative number of lymph nodes detected.
 
2. To evaluate surgical safety: the incidence of surgical transfer and the incidence of postoperative complications.

Secondary purpose of the study	Pain and cosmetic scores of patients after breast conserving surgery under a single port robotic approach.
research design	
 Randomized controlled trial
 
 non-randomized controlled study
 
 Single-arm study
 
 Other
 
 Single-center study    multicenter study
 
Whether blind:  yes  no

subject investigated	Patients undergoing breast-conserving surgery for breast cancer.
intervention study	Single-port Robot-assisted breast-conserving surgery for breast cancer.
endpoint criteria	Success rate of breast conservation surgery under single-port robotic approach
sample capacity	Total number of cases: 100; 20 in the test group; 80 in the control group

statistical analysis	Double data entry was carried out using Excel 2010, and data analysis was performed with SPSS 25.0. The normality of continuous variables and homogeneity of variance were examined by Kolmogorov-Smirnov test and analysis of variance test respectively. For continuous variables that conformed to normal distribution and had homogeneity of variance, the independent-samples t-test was adopted. For continuous variables that did not conform to normal distribution, the Mann Whitney U test was used. For categorical variables and count data, Fisher's exact test and Pearson chi square test were employed.
Study cycle	November 2024-December 2025

## 1. Research Background

Breast cancer is the second most prevalent female malignancy in China[1]. At present, the most important treatment for breast cancer is still surgical treatment[2-5]. Surgical treatment is inevitable in many cases, and with traditional surgery, it does leave a permanent scar on the chest[6]. Patients with high requirements for breast and breast aesthetic requirements are troubled by this. Studies show that young women of Asian descent (<50 years old) have more dense breasts than white women in the US[7]. So, it is more likely to the scars happen, and the scar repair after breast surgery is also more slow[8,9]. Therefore, minimally invasive breast surgery is necessary for Chinese women. Clinically, breast surgeons carry out different minimally invasive surgical methods and use different surgical approaches (such as axillary approaches) to achieve scar-free and attractive breast cancer surgery.[10,11]

The minimally invasive surgical approach enables better wound healing and less postoperative pain with the same tumor removal effect as open surgery[12]. Robotics is one of the widely used minimally invasive surgery in breast surgery, compared with open surgery, this minimally invasive technique reduces the occurrence of postoperative complications, enhances the protection of limb function, and meets the needs of patients for beauty. The study data showed that the postoperative complication rate of traditional open surgery was 7%, while the complication rate after robotic surgery was only 3.9%[13-15]. At the same time, in addition to the advantages of minimally invasive technology, robotics has its unique characteristics[16-18]. The application of robot technology makes breast surgery realize remote, digital and intelligent. Compared with the endoscopic surgery system, the robot system has a three-dimensional high-definition visual field magnified tens of times, so that the surgeon can have a clearer surgical vision, improve the surgical resolution, and increase the control of the operation. Moreover, the robots rotating wrist surgical instrument arm can rotate for 540°, enabling intuitive movement for a

more flexible and delicate operation[19]. For breast surgery with a narrow surgical area, the application of robotics is particularly important.

In 2017, robotics was first applied in breast surgery by Toesca et al[20]Since then, the application of robots in breast surgery has been further developed to form robotic prosthetic breast reconstruction and nipple-sparing mastectomy[21-23]. Compared with traditional open breast surgery, robotic breast surgery can retain normal tissue to the maximum extent, and achieve the advantages of small blood loss, less postoperative complications, postoperative symmetry, beauty and feel under the premise of complete tumor removal. However, in the clinical application process, due to the limited breast surgery area, the operation of the traditional multi-arm robot in the narrow surgery area is greatly limited, and there is the phenomenon of operating instruments and mechanical arm collision, which will lead to the failure of the advantages of the robot in breast surgery. The emergence of Single-port robot(SPr) effectively overcomes the disadvantages of multi-arm robot, not only continues the advantages of multi-arm robot surgical system, but also has advantages in minimally invasive, convenience, universality, flexibility, multi-directional operation. It is especially suitable for separation, suture, knot and other operations in a narrow space. Breast-conserving surgery has become one of the standard treatments for breast cancer due to the improved postoperative cosmetic effect, quality of life and acceptable postoperative tumor safety of breast cancer patients[24-28]. In 2024, Liao Ning, a Chinese scholar, gave an oral report on robot-assisted breast cancer breast conservation surgery at the 43rd ESSO. Considering both the completeness of lesion resection and the aesthetic integrity of breast preservation, the surgical approach of SPr approach through axillary incision is more advantageous than that of other approaches[27]。

In recent years, the domestic single-port robot surgical system has developed rapidly and its functions are increasingly perfect. The domestic Jingfeng ®SP1000 single-port robot surgical system will be used in our hospital. The public information

shows that Jingfeng ®SP1000 is the first single-port surgical robot to enter the registered clinical trial in China. Jingfeng Medical ® has cooperated with top hospitals and top experts in China to carry out in-depth clinical research and trial of all departments of single-port surgical robot. At present, Jingfeng ®SP1000 has been approved for gynecological indications, and completed registered clinical trials in urology, general surgery, thoracic surgery and other fields, successfully carried out more than 200 clinical operations, demonstrating a wide range of adaptability and excellent performance, bringing new value to scientific research and clinical fields. In addition, professor [name]'s team[29-31]. For the first time, the domestic Jingfeng ®EDGE SP1000 surgical system was used to successfully simulate the key steps of thyroid surgery in the oral thyroid surgery simulator, and realized the high-definition vision and high stability of single-arm robot surgical system, and its smart arm technology, hidden sleeve function and zero pressure anchor point technology are more conducive to ensure the operation safety, this successful practice provides a solid foundation and rich experience for single-port robot breast surgery and related clinical research. However, the safety and effectiveness of the procedure have not been fully verified, and whether the single-port robotic transaxillary breast cancer surgery is more advantageous than the multi-channel operating system (Xi and Si) is not reported. Therefore, this study aims to fill this gap and compare the efficacy and safety of open breast cancer surgery and single-port robot in transaxillary breast cancer surgery through a prospective, single-center phase II clinical cohort study, so as to provide scientific basis for clinical practice and promote the development of minimally invasive breast cancer surgery technology. To provide a theoretical and practical basis for the future application of EDGE SP1000 surgical system in breast cancer surgery. In addition, on this basis, we will systematically establish the technical system and standard for single-port robot breast cancer surgery in our hospital, and lead the formulation of domestic single-port robot-assisted breast cancer surgery standard, which is this the clinical promotion and application of surgery to lay a solid foundation

## 2. Purpose of Research

To evaluate the safety and feasibility of single-port robot in breast conserving surgery, and compare the advantages and disadvantages of single-port robot and traditional surgery in breast cancer complications, postoperative complications, perioperative recovery effect and safety of breast conserving surgery, so as to choose a more effective and safe surgical method.

## 3. Research Design

### 3.1 Overall Study Design

-Enrollment: Subjects who meet the inclusion criteria enter the study process, including SPr-breast conserving surgery or Traditional-breast conserving surgery. The choice of the two surgical methods is based on the patients economic situation and the availability of equipment.

-Preoperative hospitalization: Collect patient disease information (including mammography, breast B ultrasound, breast enhanced MRI, etc.).

-The day of operation: Record the operation time, intraoperative bleeding volume, intraoperative complications, intraoperative adverse events, etc.

-Postoperative hospitalization: Record postoperative complications (postoperative bleeding, flap or nipple areola complex necrosis, subcutaneous emphysema, infection, capsular spasm, postoperative shoulder pain and discomfort, etc.), postoperative pain score, and postoperative pathological biopsy.

-Postoperative hospital stay: Calculated based on the number of days from surgery to discharge.

[figure not shown]
-28 days after surgery: To understand the complication rate and mortality rate within 28 days after surgery.

-90 days after surgery: To understand the complication rate and mortality rate within 90 days after surgery.

-Disease-free survival at 3 years after surgery (recurrence was defined as surgical area and distant metastasis by the time from surgery to last follow-up or date of recurrence and metastasis).

-3 year overall survival (from time from surgery to last follow-up or death).

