### 4. Statistical analysis plan

#### 4.1 Sample size estimation

This study belongs to the phase II clinical study, SPr-breast conserving surgery group enrolled 20 patients, and compared with the tradition-breast conserving surgery group (60 cases), aims to evaluate the single-port robot assisted axillary breast protection in the treatment of breast cancer, later further expand the sample size according to the situation, to compare the clinical efficacy of the two methods.

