#### 4.3 Preliminary analysis

Two-person data entry was performed using Excel 2010 and SPSS 25.0 data analysis. Baseline numerical data will be described as mean, standard deviation or median and interquartile range, and baseline categorical data will be shown as percentage. Normality and homogeneity of variance of continuous variables were tested by Kolmogorov-Smirnov test and ANA variance, respectively. Independent sample t-test for continuous variables meeting normal distribution and homogeneity of variance, Mann Whitney U test for continuous variables not meeting normal distribution, and Fishers exact test and Pearson chi square test for categorical variables and count data. Primary endpoint analysis: The success rate of breast conservation surgery under single hole robot will be compared by Chi-square test (Chi-square test) with exact test if necessary. Use multiple interpolation methods to deal with missing data. Postoperative cosmetic score and postoperative pain score were calculated and analyzed according to the standard scale.

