## 10. Research progress

November 2024- -June 2025: screen the enrolled patients and complete the preliminary preparation of the project

July 2025-October 2025: Patient data are collected and processed

November 2025- -December 2025: Write the result report

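### 3-year disease-free survival does not count death, and none of the listed tests handles the censoring built into DFS and OS, which the 2025 calendar makes near-total

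*SAP*

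**What the plan says.** Section 3.1 of the SAP ends its list of assessments with two long-term outcomes. For 3-year DFS the explanation is "recurrence was defined as surgical area and distant metastasis by the time from surgery to last follow-up or date of recurrence and metastasis". For OS it is "3 year overall survival (from time from surgery to last follow-up or death". The visit table in section 3.6 has a 3-year column.

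Section 4.3 gives the tests by type of variable. Continuous variables get "Independent sample t-test for continuous variables meeting normal distribution and homogeneity of variance, Mann Whitney U test for continuous variables not meeting normal distribution". Categorical variables get "Fishers exact test and Pearson chi square test for categorical variables and count data". For incomplete data it says "Use multiple interpolation methods to deal with missing data". The scenario summary repeats the same four tests. Kaplan-Meier, log-rank, Cox regression and a censoring rule appear nowhere.

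Section 10 places screening and enrolment in November 2024 to June 2025. In July to October 2025 "Patient data are collected and processed", and the report is written in November and December 2025.

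DFS and OS are not among the primary or secondary endpoints in sections 3.8 and 4.4, and no test is tied to either by name.

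**The concern.** There are three linked defects.

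- **Event definition.** DFS counts recurrence in the surgical area and distant metastasis. A patient who dies without either has no event and leaves at last follow-up as disease-free, in an outcome called survival. The OS line directly below treats death differently.
- **No method for censored times.** DFS and OS are durations that end at an event or at last follow-up. For an event-free patient the recorded value is only the length of observation. The listed tests cannot tell that value from an event time.
- **Calendar.** Data close long before anyone reaches 3 years, so nearly every value would be an observation length.

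At stake is a survival statement for a new device that reflects when patients were operated on, or a crude event-free proportion labelled as a 3-year result.

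**Working it through.** The SAP states no survival rate, event count or significance level for DFS or OS, so there is no figure of its own to reproduce. A two-sided 0.05 level is assumed below.

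**1. Events, side by side (section 3.1).** The DFS clock stops at recurrence, metastasis or last follow-up. The OS clock stops at death or last follow-up. Applying the DFS rule literally to a death without recurrence gives: no event, time ends at last follow-up.

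**2. Follow-up available (section 10), taking surgery at about enrolment.**
- Earliest patient: start of November 2024 to end of October 2025 = 12 months.
- Latest patient: end of June 2025 to end of October 2025 = 4 months.
- Even counted to the end of December 2025, the earliest patient has 14 months.
- Three years is 36 months, so no patient has 3-year status at the report.

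**3. If the outcome is treated as a duration.** Suppose no events occur in either group, so there is no true difference. Control follow-up is uniform on 4-12 months and robotic follow-up is uniform on 4 to b months. Group sizes are 20 v 60 (section 4.1) and 20 v 80 (scenario summary).

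The chance that a control time exceeds a robotic time is θ = [12 − (4 + b)/2] / 8. Under the null, the standard deviation of the Mann-Whitney estimate of θ is √[(m + n + 1)/(12mn)]:
- 20 v 60: √(81/14,400) = 0.075
- 20 v 80: √(101/19,200) = 0.0725

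With z = (θ − 0.5)/SD, the approximate rejection rate is Φ(z − 1.96) + Φ(−z − 1.96). The last column comes from 3,000 simulated trials per setting.

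| Robotic v control follow-up (months) | θ | z (20 v 60; 20 v 80) | Approximation | Simulated Mann-Whitney p < 0.05 |
|---|---|---|---|---|
| 4-12 v 4-12 | 0.5 | 0; 0 | 5% | about 5% |
| 4-11 v 4-12 | 0.5625 | 0.83; 0.86 | 13-14% | about 12% |
| 4-10 v 4-12 | 0.625 | 1.67; 1.72 | 38-41% | 38-39% |
| 4-8 v 4-12 | 0.75 | 3.33; 3.45 | 92-93% | 97-98% |

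The approximation uses the null variance, so it runs low in the last row.

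A second simulation allowed events, with the same true DFS in both groups (3-year DFS assumed 90% or 95%; 1,500 trials per setting). With follow-up of 6-10 v 6-14 months, Mann-Whitney rejected in 95-97%, the t-test in 96-99% and log-rank in 2-8%. With 6-14 months in both groups, Mann-Whitney and the t-test rejected in about 4-6%.

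**4. If the outcome is treated as yes/no.** Fisher's test then shows no inflation: it rejected in at most 2.2% of runs in every setting of the second simulation, and with no events it cannot reject at all. The problem here is what the proportion means. With a constant hazard and an assumed true 3-year DFS of 90%, the proportion event-free at a mean follow-up of 8 months is 0.90^(8/36) = 97.7%. For 95% it is 0.95^(8/36) = 98.9%. Either would overstate the 3-year figure, because incomplete follow-up is ignored.

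**The case against.** A reader might infer that the plan will run Mann-Whitney on follow-up time and so produce false survival differences in 38-98% of trials. The document does not support that. No section assigns a test to DFS or OS, and neither is a named endpoint. The wording of 3-year DFS and 3-year OS fits a fixed-time yes/no status just as well, and that would go to chi-square or Fisher, where the inflation disappears.

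The high percentages also need robotic patients to be enrolled later. Sections 3.1 and 3.4.1 say only that the choice of operation depends on finances, patient choice and equipment availability. Unequal follow-up is therefore possible, but no enrolment dates by group are given. With equal follow-up the rate is the nominal 5%.

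It can also be said that the DFS parenthesis is awkward translation and may not be meant as a full event list, that deaths without recurrence should be few in early-stage patients aged 18 to 65, and that finer event categories such as nodal or contralateral disease may be left to a protocol. These points limit the size. They do not remove the defect: the DFS rule as written omits death where the next line names it, and on either reading the listed tests ignore incomplete follow-up. Whether 3-year outcomes would in fact be analysed in 2025 is not stated, but section 10 provides no later analysis.

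**Conclusion.** The point stands in limited form. DFS as written treats a death without recurrence as event-free. No listed method handles censoring in DFS or OS, whether they are read as durations or as yes/no status. The calendar leaves at most about 12 months of follow-up at data close for outcomes defined at 3 years.

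The size depends on choices the SAP leaves open. The 5% to 98% range for Mann-Whitney rests on hypothetical follow-up windows with no events, and the overstatement of a crude proportion rests on an assumed 3-year DFS of 90-95% and a constant hazard. The effect of omitting death cannot be sized, because the SAP gives no expected mortality.

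Only listed long-term outcomes are touched, not the primary or named secondary endpoints. Severity is minor to moderate.

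**What to change.** - In section 3.1, define the DFS event as the first of recurrence, distant metastasis or death from any cause, and state the censoring date for DFS and for OS.
- In section 4.3, add that DFS and OS are estimated by Kaplan-Meier with 95% CIs per group, and that the t-test, Mann-Whitney, chi-square and Fisher tests are not applied to them.
- Reconcile the 3-year outcomes in sections 3.1 and 3.6 with the calendar in section 10. The 2025 report would give only event counts and follow-up time per group, and the 3-year estimates would follow once 3-year follow-up is reached.

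The cost is SAP wording and a later date for the survival results. No extra patients or visits are needed, since section 3.6 already schedules the 3-year visit. The 2025 report would carry no 3-year survival claim.

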### 3.2 Technical route

### 3.3 Study population

#### 3.3.1 Inclusion criteria

- 1) The patient himself has very high requirements for beauty, and requires no scar on the chest;
- 2) No chest surgery and radiotherapy.
- 3) No contraindications to surgery and anesthesia.
- 4) Clinical I, stage of early breast cancer and the breast has an appropriate volume, can maintain a good breast shape after surgery.
- 5) Patients in the clinical period who meet the standard of breast conservation

surgery after preoperative treatment.

6) Age: 18 and 65 years old.

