### 3.8 Endpoint evaluation index

To verify the safety and efficacy of the single-port robot (SPr) in breast conserving surgery, the primary endpoint of this study was the success rate of breast conserving surgery. Successful breast-conserving surgery was determined by a negative tumor margin at least 2-3mm from normal tissue, and secondary endpoints included postoperative pain score and cosmetic score.

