#### 4.4 Effectiveness analysis

The primary endpoint of this study is the success rate of breast-conserving surgery in patients with breast cancer. The success of breast-conserving surgery was determined by a negative tumor margin at least 2-3mm from normal tissue. Secondary endpoints included surgical specimen quality, functional outcome, and quality of life (postoperative pain score, postoperative cosmetic score).

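### The margin endpoint has no scoring rule for specimens without residual tumour, although patients operated on after preoperative treatment are eligible and are pooled with the rest in an unadjusted, non-randomised comparison

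*SAP*

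**What the plan says.** **Eligibility.** Section 3.3.1 lists six inclusion items with no connecting word. Item 4 reads "Clinical I, stage of early breast cancer and the breast has an appropriate volume". Item 5 reads "Patients in the clinical period who meet the standard of breast conservation", continuing "surgery after preoperative treatment". Stage wording seems to be lost in both items, so nothing here rests on it. The reference to preoperative treatment is intact.

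**Endpoint.** Section 3.8 states: "Successful breast-conserving surgery was determined by a negative tumor margin at least 2-3mm from normal tissue". Section 4.4 repeats it: "The success of breast-conserving surgery was determined by a negative tumor margin at least 2-3mm from normal tissue". Neither mentions a specimen without tumour.

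**Analysis.** Section 4.3 states: "The success rate of breast conservation surgery under single hole robot will be compared by Chi-square test", with an exact test if needed. No section stratifies, adjusts or reports separately by preoperative treatment.

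**Allocation.** Section 3.1 states: "The choice of the two surgical methods is based on the patients economic situation and the availability of equipment". Section 3.4.1 adds physician advice and patient choice. The Scenario summary marks the study as non-randomised and not blinded.

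**Data.** The schedule in section 3.6 has tumour-related history, and tumour stage before and after surgery. It has no explicit item for preoperative treatment or pathological response.

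**The concern.** The endpoint is a distance from tumour to resection edge, so it needs a tumour. Preoperative treatment can leave none, and the definition then gives no value. The analyst would have to choose: count the patient as a success, call the patient not evaluable, or treat the margin as missing and pass it to the multiple imputation in section 4.3. In an unblinded study that choice could be made with the results in view.

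The natural choice is success, since no tumour lies at the edge. Such a patient then says nothing about surgical accuracy, which is what the comparison is meant to show. With 20 robotic patients, each one is 5% of that group.

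Nothing in the allocation balances preoperative treatment between the groups, and the planned test cannot correct an imbalance.

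The list format adds a second difficulty. If all inclusion items must hold together, every patient would need preoperative treatment, which is unlikely to be intended.

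**Working it through.** The SAP has no figure to reproduce here. It gives no expected success rate, no frequency of preoperative treatment and no rate of complete response. Section 4.1 gives group sizes of 20 and 60 without alpha, power or effect size. The Scenario summary says "Total number of cases: 100; 20 in the test group; 80 in the control group". Both control sizes are used below. Every other input is an assumption, chosen to show how the mechanism behaves.

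**Notation.** s = share given preoperative treatment; c = share of those with no residual tumour; w = s × c; p = success rate where tumour remains. If all patients without tumour are scored as successes:

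- observed success = w + (1 − w) × p
- equal w in both groups: a true difference d becomes (1 − w) × d
- unequal w, no true difference: false difference = (w_robotic − w_control) × (1 − p)

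**Equal shares (dilution).** Assume s = 20-60% and c = 10-50%. Then w runs from 0.2 × 0.1 = 2% to 0.6 × 0.5 = 30%, or 0.4 to 6 of 20 robotic patients. An assumed true contrast of 90% v 70% (two-sided 5%, pooled-variance normal approximation) becomes:

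| w | Observed difference (points) | Power, 20 v 60 | Power, 20 v 80 |
|---|---|---|---|
| 0 | 20.0 | 41.5% | 43.0% |
| 2% | 19.6 | 40.4% | 41.7% |
| 12% | 17.6 | 34.6% | 35.5% |
| 30% | 14.0 | 25.0% | 25.1% |

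**Unequal shares (false difference).** Assume p = 85%, and s = 60% robotic v 20% control.

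- c = 40%: w = 24% v 8%. Observed failure = 0.15 × 0.76 = 11.4% v 0.15 × 0.92 = 13.8%. The false advantage is 2.4 points, and 20 × 0.24 = 4.8 robotic patients are uninformative.
- c = 20%: 13.2% v 14.4%, so 1.2 points (2.4 robotic patients).
- c = 60%: 9.6% v 13.2%, so 3.6 points (7.2 robotic patients).

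With w = 30% v 5% instead, the false difference is 0.25 × 0.10 = 2.5 points at p = 90% and 0.25 × 0.20 = 5 points at p = 80%. If the imbalance is reversed, so is the sign.

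**Against sampling error.** At 20 v 60 the standard error of the difference is √(0.114 × 0.886/20 + 0.138 × 0.862/60) = 8.4 points, so 2.4 points is about 0.3 standard errors.

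**Effect of the scoring rule.** In the central case the robotic success rate reads 0.24 + 0.76 × 0.85 = 88.6% if these patients count as successes, and 85.0% if they are left out. The choice alone moves it by 3.6 points.

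**Would stratifying help?** In the central case, success among treated patients is 0.40 + 0.60 × 0.85 = 91% in both groups, and among the others 85% in both. The difference within each stratum is zero, so the false 2.4 points disappear. This needs c to be the same in both groups. Dilution within the treated stratum remains.

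**The case against.** Much of the case on the other side is fair.

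- **The effect may be small.** The inputs are assumptions, and a threefold imbalance towards the robot has no support in the SAP. Equal shares bring dilution, not bias towards either group. The central false difference is about half of one patient in 20. This stands: the size is unknown and could be near zero.
- **Other rules already remove failures.** Exclusion 4 in section 3.3.2 drops patients whose margin cannot be made negative on re-resection, and exit criterion 1 in section 3.3.3 drops robotic conversions. If few failures are left, 1 − p is below the assumed 15% and any false difference shrinks with it. This stands too.
- **A rule may exist elsewhere.** The protocol is not shown, and the pathology core laboratory list in section 7 has no content after its lead-in. That is possible, but sections 3.8 and 4.4 define the endpoint and 4.3 sets its test, so the rule belongs with them.
- **It is one case of general confounding.** That is partly so. The undefined endpoint value is a separate defect, and adjustment alone would not repair it.

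A reader might go further and infer that patients without residual tumour automatically score a negative margin. The SAP does not say so; it is silent. A reader might also describe the mix as downstaged patients pooled with untreated stage I patients. Neither description is in the text: the type of treatment and the response are not given, and the stage wording is incomplete.

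**Conclusion.** The point holds in a limited form. Three things are firm: patients may enter after preoperative treatment; the primary endpoint has no defined value when no tumour remains; and the primary comparison pools all patients without adjustment in a non-randomised, unblinded study. That scoring such patients as successes would dilute or distort the comparison is conditional on that scoring.

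No SAP figure fixes the size. Under the assumed inputs (15% failure where tumour remains, preoperative treatment in 60% v 20%, complete response 20-60%) the false difference is 1.2 to 3.6 points. At its central value that is small beside the sampling error of a 20-patient group. Dilution could matter more if such patients were common in both groups: at w = 30%, an assumed 20-point contrast would read 14 points.

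The plan should be changed because the gap concerns the meaning of its only primary endpoint and is cheap to close. There is no evidence of a large bias.

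**What to change.** 1. In 3.3.1, state that items 4 and 5 are alternatives, if that is intended, and record which one each patient meets.
2. In 3.6, add preoperative treatment and pathological response as explicit data items.
3. In 4.4, before any data are seen, state how a specimen without residual tumour is scored for the primary endpoint, and whether the imputation in 4.3 applies to it.
4. Add to the primary comparison an analysis stratified by preoperative treatment, for example by an exact or Mantel-Haenszel method.
5. Report the number without residual tumour by group, with an analysis excluding them. Label it supportive: residual tumour is seen only in the removed specimen, and a tumour-free specimen could also reflect a missed lesion, so this restriction can select on the operation.

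**Cost.** One or two added data fields, some SAP wording and one table. Strata will be small: in the example above, the 20 robotic patients split 12 and 8. The supportive analysis loses precision. With 20 × 0.76 = 15.2 and 60 × 0.92 = 55.2 patients left and 15% failure in each group, the standard error is √(0.1275/15.2 + 0.1275/55.2) = 10.3 points, against 8.4 for all patients.
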